14.2 Sponsor Responsibilities

1. General Duties
 - a. Submitting the IND application to FDA.
 - b. Obtaining both FDA and IRB approvals for the investigation before shipping the devices and drugs to any investigator.
 - c. Obtaining FDA approval and IRB approval for a supplemental application before beginning that portion of the investigation.
 - d. Selecting qualified investigators.
 - e. Ensuring proper monitoring.
 - f. Ensuring sites adhere to patient informed consent being documented and obtained.
2. Selection of Investigators
 - a. Assure selection of investigators qualified by training and experience
 - b. Shipping the investigational device only to participating investigators
 - c. Obtaining a signed investigator's agreement containing:
 - i. Investigator's curriculum vitae
 - ii. Statement of investigator's relevant experience, including dates
 - iii. Location, extent, and type of experience
 - iv. If an investigator was involved in an investigation or other research that was terminated, an explanation of the circumstances that led to the termination
 - v. Statement of the investigator's commitment to:
 - Conduct the investigation in accordance with the agreement, the investigational plan, 21 CFR Parts 50, 56, and 312, and any conditions of approval imposed by the IRB or FDA
 - Supervise all testing of the device involving human subjects
 - Ensure that the requirements for informed consent are met (21 CFR Part 50)
3. Providing investigators with the necessary information to conduct the investigation including, but not necessarily limited to:
 - a. The Protocol
 - b. Investigator Brochure
 - c. Case Report Form
 - d. Informed Consent
 - e. FDA Letter to Commence the Study

4. Refer to Section for Section 18 for Safety Reporting Requirements

14.3 Record Retention

Subject study records, correspondence files, all supporting study documentation, and reports must remain on file at the investigational site for a minimum of two years or in line with the institutional document retention policy (if longer) after the completion/termination of this study or when it is no longer needed to support a marketing application, whichever is later. The Principal Investigator must contact Thrombolex, Inc. before destroying or archiving off-site any records and reports pertaining to this trial to ensure that they no longer need to be retained on site. Thrombolex, Inc. reserves the right to have all documents shipped to its office at the end of the two-year retention period at its own cost.

15.0 DEVICE AND DRUG ACCOUNTABILITY

15.1 Bashir™ Endovascular Catheter Packaging for the IR suite/Cath lab

The Bashir™ Cather is packaged to provide protection during transportation and to facilitate introduction into the sterile environment. The shaft of the Bashir Catheter is inserted into a protective tube, mounted to a 0.3" wide x 46.5" long; .020" HDPE is inserted into a peel-pouch is shipped in a dispenser box.

15.2 Device Accountability

A packing slip will accompany all devices in each shipping box, 1 slip for multiple catheters. The site will retain the packing slips in their regulatory binder. The site should document each device and device disposition on the device accountability log provided to the site.

15.3 Drug Accountability

The sites shall provide Cathflo® Activase (Alteplase) (r-tPA) and sterile water from their respective pharmacy for use in this study. The site will document each vial and drug disposition on the drug accountability log provided to the site.

16.0 STATISTICAL CONSIDERATIONS

16.1 Sample Size Justification

The sample size selected (10) is considered to be a number sufficient to gather essential early information on the safety and performance of the device. The essential information is identified in the primary and secondary endpoints defined. The sample size will also assist in identifying additional meaningful data points, refine study endpoints, and improve study procedures before proceeding to a larger statistically powered pivotal trial.

16.2 Data Analysis

Data collected will be summarized using descriptive statistics. The study is not statistically powered for the analysis of primary endpoints. Concomitant medications will be coded using the World Health Organization (WHO)-drug dictionary and AEs will be coded using the Medical Dictionary for Regulatory Affairs (MedDRA).

16.3 Data Entry

Data will be entered into a 21 CFR 11 compliant database, electronic data capture (EDC) for this study. The site staff shall be responsible for data entry.

17.0 DATA SAFETY MONITOR

A data safety monitor will be selected to review the study conduct, feasibility data, and safety data and will adjudicate all types of adverse events reported in this study. The independent DSM shall have the final adjudication for the events. A data safety charter will be established and will be approved by the data safety monitor. Qualifications for the DSM, at a minimum, shall include current experience with catheter directed thrombolysis for the treatment of massive and submassive pulmonary emboli, management of the patient post-treatment and extensive research experience. Adherence to the study stopping criteria in this protocol will also be included in the DSM meetings in addition to following the charter.

18.0 STUDY STOPPING CRITERIA

This first-in-man study is to demonstrate safety and device success defined as the ability to use the Bashir™ Endovascular Catheter as intended for the treatment of pulmonary embolism. The treatment for pulmonary embolism in this study utilizes the Bashir™ Endovascular Catheter for the delivery of r-tPA into the pulmonary artery. The dose of r-tPA in this study is much less than the FDA approved prescribed dose (FDA approved dosing 100mg infused intravenously over two hours for massive PE versus this study dose of approximately 12mg [for unilateral PE] to approximately 14mg [for bilateral PEs] over approximately 8 hours into the PA). The study stopping criteria will be based on criteria related to bleeding, device use, and early efficacy.

18.1 General Study Stopping Rules

- 18.1.1 The Sponsor, DSM, IRBs, regulatory authorities, or the principal investigators may make recommendations to terminate the study if the safety and well-being of the subjects are in jeopardy.
- 18.1.2 If the study is terminated or suspended, prompt notification will be provided to all parties involved in the conduct of the study.
- 18.1.3 Patient enrollment may be paused or terminated early if the Sponsor or DSM determines that the potential benefits of the investigational device are unlikely to outweigh the risks associated with continuation of the trial.

18.2 Safety Study Stopping Rule

If two (2) patients undergoing the investigational procedure die or experience an unprovoked intracranial hemorrhage, confirmed by independent DSM adjudication, and did not have a protocol violation such that he/she cannot be considered as representative of the intended patient population, the study shall be paused for re-evaluation, and may be stopped.

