1.0 PROTOCOL SYNOPSIS (CONTINUED)

POPULATION	Patients 18 years of age or older who present with symptoms of acute submassive PE within 14 days of onset of symptoms will be considered for this study.
STUDY DESIGN	Prospective, non-randomized, multi-center study.
STUDY OBJECTIVE	Assess the safety and feasibility of the Bashir™ Endovascular Catheter for the administration of low dose thrombolytic for acute submassive pulmonary embolism.
SAMPLE SIZE	Up to ten (10) subjects will be enrolled and treated.
SITES	Up to five (5) sites will be qualified to participate in this study.
PRIMARY ENDPOINTS	
1. Safety: Major bleeding, as defined by International Society of Thrombosis and Hemostasis (ISTH), within 72 hours of initiation of r-tPA administration. Bleeding criteria are as follows: Major Bleeding in Non-Surgical Patients
 
 a. Fatal bleeding; and/or b. Symptomatic bleeding in a critical area or organ, such as intracranial, intraspinal, intraocular, retroperitoneal, intraarticular or pericardial, or intramuscular with compartment syndrome; and/or c. Bleeding causing a fall in hemoglobin level of 2 g/dL (1.24 mmol/L) or more or leading to transfusion of two or more units of whole blood or red cells. 
2. Feasibility: Device success defined as the ability to use the Bashir™ Endovascular Catheter as described in this protocol.

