4.2 Current Treatment Options

Anticoagulant therapies are administered to symptomatic patients while their work-ups are being completed for a definitive diagnosis of massive or submassive PE. For the treatment of massive and submassive PE, both systemic administration and catheter-directed administration of thrombolytic therapies have been utilized.⁸⁻¹⁰ However, systemic administration of thrombolytics carries a prohibitively high risk of bleeding: Up to 7% intracranial bleeds and up to 20% major bleeding rates; hence the attraction of delivering thrombolytics in much lower dosage directly into the clot to treat this potentially life-threatening condition.¹¹

Devices for percutaneous treatment of patients in whom systemic thrombolytic therapy is absolutely contraindicated have been developed and utilized. The percutaneous devices include manual thrombus fragmentation using a balloon dilatation catheter or a pigtail (off-the shelf technologies). More recently, catheters specifically created for thrombus fragmentation that produce greater fragmentation of the clot compared to off-the-shelf technologies mentioned

previously, without aspirating the clot; aspiration or suction thrombectomy devices to decrease thrombus burden; rheolytic thrombectomy where a saline jet is directed into the clot and the clot and saline are aspirated, have been introduced.^{7-10,12-14} However, there are also hazards associated with rapid clot fragmentation including hemodynamic collapse due to the distal embolization of thrombus and release of vasoactive substances.

Over the past several years a device received 510(k) clearance for its ultrasound-facilitated, catheter directed low-dose fibrinolysis using r-tPA (EKOS, Bothell WA). With this technology, the EKOS ultrasound device was used to deliver t-PA in patients with massive and submassive PE at 1mg/hour over 24 hours (unilateral PE), and 2mg/hour over 12 hours (bilateral PE). This treatment methodology achieved an absolute reduction in RV:LV ratio of 0.42 (± 0.36), the mean baseline was 1.55 (± 0.39) and at 48 hours 1.13 (± 0.2).^{15,17}

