18.4 Device Study Stopping Rules

- 18.4.1 Should it be suspected that a device caused a serious adverse event, the serious adverse event will be adjudicated by the independent DSM and the device shall be returned to the manufacturer. A root cause analysis shall be performed. The DSM will determine if the study should be stopped, temporarily suspended, or continued after each such event.
- 18.4.2 There are device malfunctions, or non-conformances, that may impact the patient and prevent treatment with an investigational device. Upon commencement of enrollment, if there are device failures that prevent three (3) patients from being treated in this study, the study shall be paused for re-evaluation. A root cause analysis will be performed to determine the cause(s) of the device failures and a corrective and preventative action will be implemented.

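### The mandatory safety pause needs two confirmed deaths or intracranial haemorrhages among at most ten patients, so it is more likely than not to fire only if the true event rate exceeds about 16%; no decision is required after a first event unless a device cause is suspected

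*Combined protocol and SAP*

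**What the plan says.** **The rule.** Section 18.2 opens with "If two (2) patients undergoing the investigational procedure die or experience an unprovoked intracranial hemorrhage, confirmed by independent DSM adjudication". It adds that the patient concerned "did not have a protocol violation such that he/she cannot be considered as representative of the intended patient population". The consequence is that "the study shall be paused for re-evaluation, and may be stopped".

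**The size of the study.** The synopsis states: "Up to ten (10) subjects will be enrolled and treated". Section 16.1 supports the number by judgement ("The sample size selected (10) is considered to be a number sufficient to gather essential early information on the safety and performance of the device"). No operating characteristic is given for the stopping rule.

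**Other routes to a pause.** Section 18.4.1 applies when a device is suspected of having caused a serious adverse event. There, "The DSM will determine if the study should be stopped, temporarily suspended, or continued after each such event". Sections 18.1.1 and 18.1.3 allow a recommendation to terminate, or a pause, but do not require either. Section 17 has the data safety monitor (DSM) adjudicate all adverse events under a charter. It does not itself call for a stop-or-continue decision after a first death or bleed.

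**Background rate.** Section 4.2 says that "systemic administration of thrombolytics carries a prohibitively high risk of bleeding: Up to 7% intracranial bleeds and up to 20% major bleeding rates".

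**The concern.** In a ten-patient first-in-man study, a trigger of two deaths or intracranial haemorrhages is reached with fair probability only when the event rate is very high. The three qualifiers (unprovoked, DSM-confirmed, no disqualifying violation) can only lower that probability, and section 3 does not define unprovoked.

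What matters in practice is what must happen after the first event. The site reports it within 24 hours (sections 13.1 and 13.5), so the signal arrives quickly. If no device role is suspected, nothing in the protocol then obliges anyone to decide whether the next patient should be enrolled.

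**Working it through.** The plan states no figure for this rule, so there is none to reproduce.

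**Inputs.** Trigger r = 2 (section 18.2). Maximum n = 10 (synopsis). Benchmark intracranial rate 7% (section 4.2, an upper figure for systemic thrombolysis). Death rate: not given, so assumed over a range. The trigger is read as a combined count of patients with either event. Requiring two of the same kind would make it fire less often.

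**Chance that the rule fires.** P(X ≥ 2) = 1 − (1−p)^10 − 10p(1−p)^9. At p = 0.07 this is 1 − 0.4840 − 0.3643 = 0.1517.

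| Combined event rate | P(at least 2 of 10) | P(at least 2 of first 9) | P(at least 1 of 10) |
|---|---|---|---|
| 5% | 8.6% | 7.1% | 40.1% |
| 7% | 15.2% | 12.7% | 51.6% |
| 10% | 26.4% | 22.5% | 65.1% |
| 15% | 45.6% | 40.1% | 80.3% |
| 20% | 62.4% | 56.4% | 89.3% |

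The third column is the chance that the rule fires while at least one patient is still to be treated. Solving P(X ≥ 2) = 0.5 gives p = 16.2%; solving for 0.8 gives p = 27.1%.

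**Adding deaths.** With 7% intracranial haemorrhage and an assumed independent death rate d, the combined rate is 1 − 0.93(1−d).

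| Assumed d | Combined rate | P(rule fires) |
|---|---|---|
| 0% | 7.00% | 15.2% |
| 2% | 8.86% | 22.0% |
| 5% | 11.65% | 32.8% |
| 10% | 16.30% | 50.3% |

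**Number treated at a 20% rate.** The expected number treated up to the second event or the cap of ten is the sum, for k = 0 to 9, of the chance of at most one event in the first k patients: 1 + 1 + 0.960 + 0.896 + 0.819 + 0.737 + 0.655 + 0.577 + 0.503 + 0.436 = 7.6. The last term also gives the chance that the second event falls within the first nine patients: 1 − 0.436 = 56.4%.

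**A first-event hold at low rates.** 1 − (1−p)^10 is 9.6% at 1%, 18.3% at 2% and 26.3% at 3%.

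**The case against.** **The benchmark is borrowed.** A reader might infer that the protocol itself declares 7% unacceptable for this treatment. It does not. The figure is an upper value for systemic thrombolysis, and section 18.0 contrasts the approved 100 mg with about 12 to 14 mg here. This stands: 7% only gives a sense of scale.

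**Deaths are counted too.** Using the intracranial rate alone sets mortality to zero, so 15.2% is a floor in that respect. This also stands. An added death rate of roughly 10% would be needed to bring the rule to even odds.

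**The rule is not useless.** A reader might take 2/0.20 = 10 to mean that the whole study would be treated before the second event at a 20% rate. That formula ignores the cap of ten; the expected number is 7.6, and the rule fires 62.4% of the time. The figures do not support saying that the rule gives almost no protection.

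**A first event may already need a decision.** Section 18.4.1 needs only suspicion of a device cause. The catheter delivers the r-tPA, Table 3 lists hemorrhage among device-related events, and Table 6 defines relatedness by agent or procedure. Some bleeds would therefore come under 18.4.1. The gap is limited to events with no suspected device role.

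**Unseen and discretionary safeguards.** The DSM charter may require a first-event review. Ten patients over nine months (section 6.4.1) is about one a month, which leaves time to use section 18.1.3. The documents therefore do not show that a first event would go unreviewed. They show only that the protocol does not require a decision.

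**Weak rules are inherent at n = 10.** Any count rule here has poor operating characteristics, and choosing two events over one is a trade-off, not an error. That is fair, but a brief hold for a decision costs far less than a stop, so a lower count is affordable for it.

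**Conclusion.** The point holds as a cheap improvement to a defensible design choice. The mandatory pause fires with probability 8.6% to 26.4% at combined event rates of 5% to 10%, and is more likely than not to fire only above about 16.2%. At the 7% benchmark the range is 15.2% with no added deaths to 50.3% with an assumed 10% death rate.

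For a first death or intracranial haemorrhage with no suspected device role, the protocol text leaves any pause to discretion. Whether the charter closes that gap cannot be checked.

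The figures assume ten treated patients, independent events at a constant rate, a combined count, and that every event qualifies. Fewer patients would lower the probability of firing (at 7%, 10.4% with eight patients and 4.3% with five), as would any event that fails a qualifier.

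**What to change.** Add to section 18.2, and align the DSM charter: the first death or intracranial haemorrhage, whatever its attribution, puts new enrolment at all sites on hold from the site's 24-hour SAE report, until the DSM documents a decision to continue. Adjudication then decides whether the hold is lifted, not whether it starts. Keep the two-event trigger for the full re-evaluation. This extends the single-event decision that section 18.4.1 already uses. It concerns enrolment only, not the treatment of any patient.

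The cost is wording in two documents and a short hold that may prove unneeded (probability 9.6%, 18.3% or 26.3% at true rates of 1%, 2% or 3% over ten patients). At about one patient a month, that is tolerable.

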18.3 Efficacy Study Stopping Rule

Should the treatment not achieve a reduction in RV:LV ratio as measured by CT at 48 hours by at least 0.06 compared to baseline, in three of the first three patients, the study shall be paused for re-evaluation.

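### The safety pause in Section 18.2 can disregard a confirmed death or intracranial hemorrhage on an undefined judgement that the patient was not representative

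*Combined protocol and SAP*

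**What the plan says.** Section 18.2 of the protocol sets the threshold: "If two (2) patients undergoing the investigational procedure die or experience an unprovoked intracranial hemorrhage". Two conditions follow. The first is that the event is "confirmed by independent DSM adjudication". The second concerns the patient, who must be someone who "did not have a protocol violation such that he/she cannot be considered as representative of the intended patient population". If the threshold is met, "the study shall be paused for re-evaluation, and may be stopped".

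The synopsis caps the study: "Up to ten (10) subjects will be enrolled and treated". Section 16.2 states that "The study is not statistically powered for the analysis of primary endpoints", and no operating characteristics are given for the safety rule.

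Other provisions bear on the point:
- Section 18.1.1 lets several parties recommend termination. Section 18.1.3 allows the sponsor or the DSM to pause enrollment at their discretion.
- Section 18.4.1 requires a DSM decision after each serious adverse event that the device is suspected of causing.
- Section 17.0 gives the DSM final adjudication of events, calls for a charter, and puts adherence to the stopping criteria on the agenda of DSM meetings.
- Section 13.5 requires serious adverse events to be reported within 24 hours, whatever their cause.

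**The concern.** Section 18.2 is the only rule in the protocol that turns a count of deaths or intracranial hemorrhages into a mandatory pause. Its second condition takes some treated patients out of that count, and the section leaves the condition open in three respects. It lists no qualifying violations and does not confine them to eligibility errors. It names no one to judge representativeness, since DSM confirmation attaches to the event. It gives no timing.

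No advance or outcome-blind classification is described, so the natural moment for the judgement is when an event is being considered for the count. Several exclusion criteria in Section 6.3.2 are themselves matters of opinion: no. 12 (clinician's view of catastrophic bleeding risk), no. 25 (investigator's view of bleeding risk in morbid obesity) and no. 29 (general suitability). After a hemorrhage it could be argued that one of these was met at entry.

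At stake is whether enrollment in a first-in-man study can continue, with no mandated review, after two confirmed deaths or hemorrhages. A fatal event in a patient who should not have been enrolled is also a reason to look again at screening, which is the kind of question a pause exists to answer.

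**Working it through.** The plan states no trigger probability, so there is no figure to reproduce. The point rests on the wording; the arithmetic only illustrates its size.

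**Step 1: the count.** The threshold is 2. If two treated patients have confirmed events and one is set aside, the count is 2 − 1 = 1. Since 1 < 2, Section 18.2 mandates nothing.

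**Step 2: given exactly two events.** Let each event have an independent chance q of being set aside (assumed). The pause then triggers with probability (1 − q)², against 100% if all events count:
- q = 10%: 81%
- q = 20%: 64%
- q = 30%: 49%
- q = 50%: 25%

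**Step 3: over the whole study.** From the documents: up to 10 treated, threshold 2. Assumed: v patients with a disqualifying violation and event risk a, m = 10 − v others with risk b, independent events, all 10 treated, and every violator's event set aside.

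All events counted:
P = 1 − (1−a)^v (1−b)^m − [v·a(1−a)^(v−1)(1−b)^m + (1−a)^v·m·b(1−b)^(m−1)]

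As written:
P = 1 − (1−b)^m − m·b(1−b)^(m−1)

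One violator, uniform 5% risk:
- All counted: 1 − 0.95^10 − 10(0.05)(0.95^9) = 1 − 0.59874 − 0.31512 = 0.0861
- As written: 1 − 0.95^9 − 9(0.05)(0.95^8) = 1 − 0.63025 − 0.29854 = 0.0712

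Two violators at 30%, eight others at 5%:
- All counted: no event 0.7² × 0.95^8 = 0.32508; one event 0.41551; P = 1 − 0.32508 − 0.41551 = 0.2594
- As written: 1 − 0.66342 − 0.27933 = 0.0572

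| Violators (risk) | Others (risk) | All counted | As written |
|---|---|---|---|
| 1 (2%) | 9 (2%) | 1.6% | 1.3% |
| 1 (5%) | 9 (5%) | 8.6% | 7.1% |
| 2 (10%) | 8 (10%) | 26.4% | 18.7% |
| 1 (30%) | 9 (5%) | 16.1% | 7.1% |
| 2 (30%) | 8 (5%) | 25.9% | 5.7% |

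The clause can only lower the chance of a pause. By how much depends on the number of violators and on their excess risk, and the documents give neither.

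**Step 4: do other provisions supply the same trigger?** Sections 18.1.1 and 18.1.3 carry no representativeness condition but are discretionary. Section 18.4.1 has no such condition either, and it obliges the DSM to decide, but only where the device is suspected. A hemorrhage attributed to r-tPA, or a death attributed to the embolism itself, need not meet that test. None of the three mandates a pause on a count of events.

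**The case against.** The best defense is that limiting an automatic trigger to the intended population is a legitimate choice and that little oversight is lost. Serious adverse events are reported within 24 hours, the DSM adjudicates every adverse event, and Section 18.4.1 demands a decision after a single device-suspected event, sooner than a count of two. The DSM charter, which is not among the documents, may define the violations and who decides on them. All of that stands. What is lost is the automatic pause, not oversight as such.

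Several stronger readings are tempting, and the documents do not support them:
- **Every wrongly enrolled patient is dropped.** The clause reaches only a violation that makes the patient non-representative. A lesser eligibility deviation still counts.
- **The judgement is made after the event.** This is an inference. The section gives no timing; it merely fails to require a judgement made in advance or blind to outcome.
- **The sibling rules show that the safety rule is anomalous.** Section 18.3 applies "in three of the first three patients, the study shall be paused for re-evaluation" and is silent on violators. Section 18.4.2 applies "if there are device failures that prevent three (3) patients from being treated in this study, the study shall be paused for re-evaluation", so it concerns patients who could not be treated. Neither is a close comparator.
- **The patients removed are those most likely to bleed.** Some may be, but a disqualifying violation could equally be hypotension or vasopressor support (Section 6.3.2, nos. 15 and 16), where a death may reflect the underlying embolism.
- **The chance of a pause falls from 26% to 6%.** That pair assumes two violators in ten, each at six times the risk of the others. Section 14.1 (item 12c) does not permit deviations except to protect the patient, so the true number may be small.

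**Conclusion.** The point holds in a limited form. As written, a confirmed death or unprovoked intracranial hemorrhage can be left out of the count through a condition with no defined content, judge or timing, and two events with one set aside mandate no pause. That follows from the wording and needs no assumption.

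The effect on the chance of a pause does rest on assumptions. It is slight with one violator at the same low risk as everyone else (8.6% versus 7.1% at a 5% risk) and large with two high-risk violators (26% versus 6%). Neither is an estimate for this trial.

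Because Section 18.2 leads first to a pause, and only possibly to a stop, a representativeness question can be settled in the re-evaluation without loss. This is a worthwhile, low-cost improvement. It does not show that the study is unmonitored.

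**What to change.** In Section 18.2, delete the condition that the patient "did not have a protocol violation such that he/she cannot be considered as representative of the intended patient population" from the trigger, so that every treated patient with a DSM-confirmed event counts. Add one sentence: during the re-evaluation, the DSM considers any protocol violation, including eligibility, when deciding whether the study may resume. Carry the same wording into the DSM charter.

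If the sponsor prefers to keep the condition, a weaker alternative is to list the qualifying violations in advance and name the DSM as judge. That would curb outcome-aware exclusion but would still leave some events in treated patients uncounted.

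The cost of the main change is a short edit to Section 18.2 and the charter, plus an occasional extra pause that the DSM can lift. No dose or patient-management rule is affected.
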